1.0 Research Introduction

Title of Project

A Comparison of the Efficacy of Sphenopalatine Ganglion Block (SPGB) with 5% Lidocaine and Epidural Blood Patch (EBP) for the Treatment of Post-Dural Puncture Headache (PDPH)

NCT# 03112720

Principal Investigator

[name], DDS

Sub-Investigators

[name] MD, [name] MD, [name] MD, [name] MD
(Administrative Assistant)

Funding Source

Department of Anesthesiology

1. Purpose

To compare the sphenopalatine ganglion block (SPGB), a local anesthetic technique that is facile to perform and carries fewer potential side effects, to the traditional, more invasive, epidural blood patch (EBP) for the treatment of post-dural puncture headache (PDPH). The SPGB is experimental while the EBP is considered to be the standard of care.

1.1. Objectives

- 1.1.1. To compare subjects who present with PDPH and are randomized into one of two treatment groups whether the SPGB technique is not inferior to the traditional EBP in treating their symptoms.
- 1.1.2. To follow subjects who initially present with PDPH to determine the efficacy of either technique in maintaining a symptom-free period.
- 1.1.3. To compare patients' experiences with the SPGB as compared to the EBP.

1.2. Hypotheses

- 1.2.1. There will be no appreciable difference in the amelioration of PDPH symptoms with the SPGB technique as compared to the EBP.
- 1.2.2. Both the SPGB and the EBP will maintain similar symptom-free periods.
- 1.2.3. The patients will experience less subjective discomfort with the SPGB as compared to the traditional EBP.

2. Background and Significance

Dural punctures may be intended or unintended following instrumentation of the spine when administering neuraxial anesthesia or performing diagnostic studies such as lumbar punctures and myelograms. As many as 40% of patients may complain of frontal and nuchal headache several hours after dural puncture (1). Furthermore, patients complain of diplopia, loss of hearing, nausea, and vomiting. Symptoms may be self-limited, though the time range varies. Significant morbidity can be observed during this interim as patients remain bed-ridden, missing time from work and enjoyment with their families. Conservative treatment measures include maintaining a supine posture, hydration with fluids, caffeine intake, and pain control

with traditional oral and parenteral medications (2) until the symptoms subside. When an unintentional dural puncture occurs during epidural catheter placement, the catheter can be left *in situ* with a low infusion of saline to ameliorate the symptoms partially.

Several theories exist to explain PDPH. Cerebral spinal fluid surrounds the brain and the spinal cord, all of which is surrounded by the dura mater. Traditionally, it was thought that following dural puncture, the leakage of cerebral spinal fluid (CSF) causes the brain that is usually suspended in this fluid to “sag”, an action that exerts traction on the meninges, which in turn causes headache (3-5). Recent studies have questioned this as the sole mechanism since any leakage would be slow, and would not explain the stark difference in symptoms from the supine to orthostatic positions (6). Instead, these symptoms likely share an etiology with other so-called “neurovascular headaches”. In the intact nervous system, CSF and the brain tissue exert pressure on the vasculature. This pressure is sufficient to cause collapse of the venous side of the circulation, a phenomenon known as “subdural venous collapse”. Following dural puncture, CSF pressure, which is normally greater than atmospheric pressure, drops as it tends to equalize through this extradural communication. The decreasing CSF and tissue pressures release the subdural venous collapse, allowing vasodilation. Furthermore, since the dural puncture turns the usually closed system into an open one, CSF pressure becomes dependent on the patient’s position, dropping significantly when sitting upright or standing. The dura is exquisitely sensitive to pain in the very areas surrounding blood vessels. The vasodilation triggers nociceptive nerve endings, which accounts for the exquisite pain from neurovascular headaches such as PDPH (6).

The EBP has traditionally been the definitive mode of treatment in patients with PDPH. This intervention involves the autologous transfusion of a patient’s blood from a sterile peripheral site into the epidural space. Several studies have established the EBP as standard of care for PDPH. A randomized, controlled clinical trial has showed that EBPs resolve PDPHs after one week in 84% of patients compared to 14% with placebo (7). Another prospective, randomized, double-blinded trial compared EBP to conservative management (fluid replacement, non-steroidal anti-inflammatory drugs, and caffeine) for the treatment of PDPH. (8). These authors found that when treated conservatively patients with PDPH noted little to no change in headache, as reported on a visual analog scale (VAS). Their headaches rated 8.2 ± 1.4 both before and after treatment. In the group who received an EBP, patients reported a decrease in headache from 8.0 ± 1.6 to 0.7 ± 0.16 . The authors further state that “The epidural blood patch represents the first choice treatment of PDPH no matter the etiology, being significantly superior to the conventional treatment which did not affect pain scores” (8). These studies have helped establish the EBP as a standard of care for PDPH. It now appears as a listed treatment for PDPH in common physician reference resources such as UpToDate® (Waltham, MA) (9).

Originally, the EBP was thought to act through a tamponade effect, plugging the dural defect and preventing the further leakage of CSF. As noted above, this is unlikely the true mechanism as patients often report immediate relief, which could not be explained by cessation of the minute flow of CSF. The more contemporary explanation is that the EBP does in fact plug the dural tear, but in doing so, it prevents the equilibration of CSF pressure with the atmospheric pressure. Injection of blood into the epidural space immediately raises

the CSF pressure within the closed spinal canal space and thus causes reflex cerebral vasoconstriction. Consequently, subdural venous collapse is restored and the headache subsides.

Although the EBP has been proven to be one effective treatment for PDPH, it is an invasive procedure and carries the same risks as those associated with the inciting event. Infections, subdural and epidural hematoma, needle trauma, and back pain have been described (10,11), in addition to a possible second dural puncture. Furthermore, the procedure requires the physician to be adept at the epidural injection technique, which usually limits treatment to anesthesiologists.

Given the purported neurovascular etiology of PDPHs, patients who suffer from this condition have been successfully treated with nerve blocks for immediate relief (12). We had proposed targeting the sphenopalatine ganglion based on the success of manipulating the trigeminal-autonomic arc for treating cluster headache, a type of neurovascular headache. Briefly, this reflex arc describes an afferent limb that includes trigeminal nerve fibers in the perivascular area of cerebral circulation. When stimulated, these neurons activate the efferent limb, the parasympathetic fibers within the greater superficial petrosal nerve, which in turn causes vasodilation (13). In neurovascular headaches, a triggering mechanism causes initial vasodilation which irritates the dura and stimulates the afferent limb of this arc. In PDPH, the equalization of pressure between the CSF and the atmosphere acts as a trigger. The parasympathetic efferent limb of this reflex causes vasodilation, which in this case is deleterious since it provides positive feedback to this reflex loop, causing continued headache. Blockade of the synaptic communication in the SPG would terminate this loop, and is the proposed pathophysiological mechanism by which neurovascular headaches are treated.

Our recent literature review has suggested that there are multiple techniques for performing the sphenopalatine ganglion block. A proven method for performing the block involves using a cotton tip applicator to place lidocaine gel in the middle posterior pharynx followed by administration of 1 mL of 4% lidocaine solution through the plastic channel of the applicator, all simply by placing the soft, flexible, cotton-tip applicator into the nares (14). This technique of transmucosal application of local anesthetics was proposed by Lebovits et al. (15) and others (16). The side effects associated with SPG blocks are minimal, often limited to the bitter taste of the anesthetic solution. The theoretical rare risks of anaphylaxis and severe epistaxis exist, but have not been described in the literature.

The SPGB has been described in the literature for the treatment of cluster headaches and is recognized as a treatment for this condition when other modalities fail (17-20). A study has investigated its use for the treatment of PDPH (21). Twenty-eight patients with PDPH were offered a SPG block prior to EBP. Nineteen of 28 patients noted relief and only 9 patients eventually needed an epidural blood patch after 1 week. Moreover, most patients (~93%) noted relief of headache at and beyond 72 hours following the procedure significantly decreasing morbidity during the otherwise symptomatic period. In this pilot study, approximately 68% of patients were saved from having to undergo the invasive EBP in favor of a more cost-effective and less invasive technique (21). This study has helped establish the

sphenopalatine ganglion block as a standard of care for the treatment of PDPH, especially when other modalities fail or are not preferred by the patient. The SPGB appears as a treatment in the common physician reference resource UpToDate® (Waltham, MA) for the treatment of adverse effects of neuraxial anesthesia (22).

3. Research Design and Methods

We propose to treat patients suffering from a severe and incapacitating headache resulting from dural puncture. Both the EBP and SPGB therapies have been shown to reduce the intensity of PDPH. The design of this study seeks to determine the duration of relief associated with both therapies and to compare the patient's satisfaction with both techniques.

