3.2. Study Design

3.2.1. Type

This is a non-inferiority trial comparing the SPGB to the EBP for the treatment of PDPH. The study is not blinded to the subject or investigator. Due to the nature of the procedure and the anatomical site of intervention, both will know which method they are receiving or delivering. We acknowledge this as a limitation of our study but reiterate that blinding one or both parties is not feasible.

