3.6. Sample Size Justification

We derive data for calculation of the sample size from the prior studies noted above. In the control group (Table 7, Group 1, EBP) we predict a success rate of 84% as noted by van Kooten et al. (7). In the treatment group (Table 7, group 2, SPG block) we predict a success rate of 68% based on our pilot study (15). If therefore there is a true 16% (84% - 68%) in favor of the EBP group then 210 subjects are required to be 90% certain that the upper limit of a one-sided 95% confidence interval will exclude a difference in favor of the EBP group of more than 33%. This calculation was performed using the formula below (Table 9 and Equation) using an online calculator <https://www.sealedenvelope.com/power/binary-noninferior/>).

Our chosen non-inferiority limit d of 33% means that we believed saving 67% (100% – 33%) of patients from the invasive EBP in favor of the non-invasive, cost-effective SPG block would be clinically relevant.

Table 9. Values used for determination of sample size

Variable	Description	Value
n	sample size	210
ϕ^{-1}	cumulative distribution function of a standardized normal deviate	n/a
α	significance level, alpha	0.05
β	false negative rate, beta, where power $(1 - \beta) = 0.90$	0.10
π_s	success rate in control group	0.84
π_e	success rate in treatment group	0.68
d	non-inferiority limit	0.33

Equation. Sample size calculation for a binary outcome non-inferiority trial

$$n = \left(\phi^{-1}(\alpha) + \phi^{-1}(\beta) \right)^2 \times \frac{\pi_s \times (100 - \pi_s) + \pi_e \times (100 - \pi_e)}{\pi_s - \pi_e - d^2}$$

4. Study Variables

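### Hypothesis 1.2.1 (no appreciable difference) matches neither the non-inferiority objective nor the 84% versus 68% planning rates, and neither a met margin nor the tests in section 5.2 could support it

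*Combined protocol and SAP*

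**What the plan says.** The protocol describes its main comparison in four ways.

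- **Hypothesis (1.2.1):** "There will be no appreciable difference in the amelioration of PDPH symptoms with the SPGB technique as compared to the EBP". The word appreciable is not defined and is not tied to any margin.
- **Objective and design (1.1.1, 3.2.1):** the objective asks whether SPGB is not inferior to EBP, and the design section states "This is a non-inferiority trial comparing the SPGB to the EBP for the treatment of PDPH".
- **Sample size (3.6):** for EBP "we predict a success rate of 84" percent, and for SPGB "we predict a success rate of 68% based on our pilot study". The section continues: "If therefore there is a true 16% (84% - 68%) in favor of the EBP group then 210 subjects are required". The stated aim is 90% certainty that the "upper limit of a one-sided 95% confidence interval will exclude a difference in favor of the EBP group of more than 33" percent. The margin is justified by the share of patients who would be spared an EBP.
- **Analysis (5.2):** the Mann–Whitney U test for VAS scores and Student's t-test for normally distributed variables, with significance at p ≤ 0.05. It contains no non-inferiority bound, no confidence interval, no analysis of a success proportion, and no statement of how a result that is within the margin but significantly worse would be read.

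**The concern.** A hypothesis of no appreciable difference sits beside a plan that expects SPGB to be 16 points worse and would accept a deficit of up to 33 points, about twice that. These are different claims. The margin argument in 3.6 is a trade-off: some loss of efficacy is accepted to avoid an invasive procedure. Hypothesis 1.2.1 is a claim of similar efficacy.

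Because 5.2 does not say how the main question will be decided, two unsound conclusions are left open. A met margin could be taken as confirming 1.2.1, or a p value above 0.05 could be. The protocol treats EBP as the standard of care, so if EBP does have an advantage of the size assumed in 3.6, either conclusion would mislead readers who are choosing between the procedures.

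**Working it through.** **Inputs.** From 3.6: EBP 0.84, SPGB 0.68, margin 0.33, one-sided α 0.05, power 0.90. Assumed: 1:1 allocation (3.2.2 gives no ratio) and a two-sided reading of the 0.05 level in 5.2. Group size: 3.6 reads as 210 in total, while 5.1 speaks of 210 completing each group, so both are shown.

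**Step 1: reproduce the plan's figure.** n per arm = (z₀.₉₅ + z₀.₉₀)² × [0.84×0.16 + 0.68×0.32] / (0.33 − 0.16)² = (1.645 + 1.282)² × 0.352 / 0.0289 = 104.3. Rounded up, this is 105 per arm, or 210 in total, which agrees with 3.6. (The equation as printed squares only d and would give a negative n; squaring the whole denominator gives the stated figure.)

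**Step 2: what a met margin shows.** At 105 per arm, SE = √(0.352/105) = 0.0579. The margin is met when the observed EBP advantage is below 0.33 − 1.645×0.0579 = 0.235. An observed deficit of up to about 23 points would therefore pass, which is not evidence of no appreciable difference.

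**Step 3: what a non-significant p value shows.** A two-sided 5% test on the proportions needs an observed difference above about 1.96×0.0579 = 0.113. With a true 16-point deficit, exact enumeration gives a significant result in 78.5% of trials, so about 21.5% would be non-significant although the planned deficit is real.

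**Step 4: how often both results occur together.** At 105 per arm, an observed EBP advantage between about 11.3 and 23.5 points is both within the margin and significantly in favour of EBP. At 210 per arm, SE = √(0.352/210) = 0.0409 and the zone is about 8.0 to 26.3 points. Exact enumeration of two binomials at 84% versus 68%, with non-inferiority as difference + 1.645 SE < 0.33 and superiority as pooled z above 1.96, gives:

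| Per arm | Non-inferior | EBP significantly better | Both |
|---|---|---|---|
| 105 | 90% | 78% | 69% |
| 210 | 99% | 97% | 97% |

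At 105 per arm, 0.6875/0.9029 = 76% of non-inferior results would also show EBP significantly better. With Fisher's exact test for superiority, the joint figures are 64% and 96%.

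**Step 5: dependence on the SPGB rate.** With EBP held at 84% and 105 per arm:

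| True SPGB rate | Non-inferior and significantly worse |
|---|---|
| 68% | 69% |
| 72% | 54% |
| 76% | 30% |
| 80% | 11% |

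The 68% comes from 19 of 28 pilot patients (section 2). The Wilson 95% interval for 19/28 runs from 49% to 82%, so all four rows are compatible with the pilot.

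**Step 6: what the rates measure.** In section 2, the 84% is headache resolution at one week and the 68% is patients who had not needed an EBP after one week. The trial scores symptoms at 30 and 60 minutes and at 24 and 48 hours (3.2.3).

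**The case against.** The strongest reply is that sizing a non-inferiority trial on an assumed deficit is legitimate, and that 1.2.1 is informal wording for a non-inferiority aim stated properly in 1.1.1 and 3.2.1. The first part stands. The second is plausible, but nothing links appreciable to 33 points, and 5.2 does not carry the non-inferiority aim into an analysis.

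Three further objections also stand and limit the point:

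- The 33-point criterion appears only in the sample-size section. The probabilities above therefore describe a bound and a test on proportions that 5.2 does not name. They cannot be carried over to the VAS tests, because no SPGB mean or SD is given.
- The hypothesis concerns symptom relief, which this trial follows to 48 hours, while the planning rates are one-week figures. The same pilot reports relief in about 93% of patients at and beyond 72 hours. A 16-point deficit at one week does not establish that the authors expect one at 48 hours.
- A reader might infer that a met margin is going to be reported as no difference. No section says so, and the difference tests in 5.2 could themselves show an EBP advantage.

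**Conclusion.** The mismatch is in the text and holds whatever the true rates are: neither of the results discussed here, a met margin or a p value above 0.05, could support 1.2.1 as worded. Following 5.2 as written would not deliver the non-inferiority conclusion either, because a difference test cannot establish it.

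The size is conditional. At 84% versus 68%, with 1:1 allocation and the two procedures set out above, the joint result has probability about 69% at 105 per arm and 97% at 210 per arm. A reader might infer that the trial will usually show EBP significantly better while claiming non-inferiority. The documents do not support that as an unconditional statement. It requires the SPGB rate to be close to 68% (at 105 per arm the probability is already 30% at 76%), it uses tests the plan does not specify, and it takes one-week rates as a guide to a 48-hour trial. What can be said is that, on the protocol's own planning rates, this is the most likely single outcome, and the plan does not say how to read it.

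**What to change.** 1. Restate 1.2.1 as: the SPGB success rate is less than 33 percentage points below the EBP rate. This states the margin that 3.6 already uses; it does not endorse the size of that margin.
2. In 5.2, make the difference in success proportions (EBP minus SPGB) the primary analysis. Define success and its time point from the data already collected. Compare the upper one-sided 95% bound with 33 points, and report the two-sided 95% confidence interval beside it.
3. State in 5.2 that if the margin is met but the two-sided interval excludes zero in favour of EBP, the report will say that SPGB is within the margin but less effective than EBP. Neither a met margin nor p > 0.05 will be described as no difference.

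The cost is one added analysis and one endpoint definition, so this is more than a wording change, and the permitted conclusion becomes less favourable to SPGB. No change to the sample size, procedures or visits is needed for this point.

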3.1. Subject selection and enrollment considerations

3.1.1. Subject recruitment

Patients who suffer from headache following dural puncture may present following neuraxial procedures such as epidural anesthesia, diagnostic lumbar puncture, diagnostic radiographic studies to physicians in several departments (**Table 1**).

Table 1. Procedures that may result in PDPH and the respective departments to whom suffering patients may present

Recent procedure	Presenting department
Epidural or spinal anesthesia	Anesthesiology or Pain Medicine (division of Anesthesiology)
Epidural steroid injection	Pain Medicine
Diagnostic lumbar puncture	Medicine, Pediatrics, Neurology, Emergency Medicine (ER) RWJUH
Myelogram	Neurology

The members of the respective departments will be informed of this study for enrollment of patients. For the purposes of the initial referral, all patients meeting minimal criteria for PDPH (**Table 2**) will be considered. These criteria for referral will be published by electronic mail to the members of the aforementioned departments. Physicians who seek to make a referral will do so by contacting the Pain Medicine physician-on-call. This on-call physician is available continuously (24 hours per day, 7 days per week) by mobile telephone. The Pain Medicine physician-on-call will receive the demographic information of this patient in the hospital and inform the principle investigator or his designee for enrollment pursuant to criteria outlined in the next section.

Table 2. Minimum criteria for initial referral into study

Criterion
A neuraxial procedure within the past 7 days
Postural headache that improves with supine position
Absence of other more likely etiology of headache

3.1.2. Inclusion Criteria

We will include patients with a moderate or severe PDPH classification, modified from van Kooten et al. (7) Complete inclusion criteria follows (Tables 3–5)

Table 3. PDPH classification

Classification	Definition
Absent	no headache
Mild	postural headache with some restriction of daily activities but without confinement to bed and without associated symptoms
Moderate	postural headache with confinement to bed for at least part of the day OR postural headache with associated symptoms restricting daily activities
Severe	postural headache with confinement to bed for entire day with associated symptoms

Table 4. Symptoms associated with PDPH

Symptoms
Nausea and/or vomiting
Dizziness
Hearing loss, hyperacusis, or tinnitus
Photophobia, diplopia
Nuchal pain or stiffness

Table 5. Inclusion criteria

Criteria
Moderate to severe PDPH (Table 3) for greater than 24 hours, but not more than 7 days after the initial procedure
Men, women, and children ages 13–92
Consent to participate in this study

3.1.3. Exclusion criteria

Criteria to exclude patients are listed (**Table 6**). Urine pregnancy tests are standard of care for all women of child bearing age prior to any anesthesia procedures. We note that pregnancy is one of our exclusion criteria. Many of the patients we seek to enroll in this study will have received neuraxial anesthesia for childbirth. Since a urine pregnancy test is not reliable in post-partum women owing to residual circulating levels of the beta subunit of human chorionic gonadotropin hormone (β -hCG) leading to a false positive result (23), any woman who complains of PDPH within 7 days of delivery will be considered not pregnant and thus be eligible for our study. All other women of child bearing age will require a negative urine pregnancy test result within the last 7 days. If no pregnancy test was completed prior to referral to this study, the patient will be required to undergo one prior to randomization. Any patient who has a positive pregnancy test or refuses to undergo this test will be excluded from the study. The pregnancy test will be billed as part of the routine work up involved with the standard of care.

In patients receiving antithrombotic or thrombolytic therapy, we will use the most recent guidelines from the American Society of Regional Anesthesia Practice Advisory (24) to determine whether the patient may undergo neuraxial anesthesia. Any patient who would be unfit for epidural instrumentation will be excluded prior to randomization.

We will exclude non-English-speaking patients in this study. While both procedures could potentially be performed in patients regardless of language proficiency, this study will specifically assess the patients' symptoms such as pain, nausea, and discomfort among others as listed in (Table 8). These assessments would need to be made contemporaneously during the procedure, which can be difficult when using a telephone translator. There would be a delay in receiving a response; moreover, the patient would not be able to hold a telephone handset when assuming the correct posture and position for these sterile procedures.

Table 6. Exclusion criteria

Criteria
Age less than 13
Non-English-speaking
Pregnancy
Allergy to lidocaine or lidocaine-containing ointments or solutions
Heart disease with New York Heart Association (NYHA) Functional Classification II or greater
Current treatment with lidocaine patch or other topical or depot vehicle for chronic pain
Presence of a spinal cord stimulator, intrathecal pump, or other implanted device in the spine
Platelet count < 100,000/ μ L
Sepsis
Skin or soft tissue infection overlying lumbar spine
Sinusitis requiring the current use of antibiotics
Nasal polyps
Nasal surgery within the past 7 days
Neurological event including stroke, intracranial hemorrhage, epidural hematoma, or other event causing a focal deficit within the past 30 days
Current anticoagulant therapy contraindicating epidural injection
Prior treatment with SPG block or EBP for this presenting condition

All inclusion criteria (table 5) and exclusion criteria (table 6) will be ascertained from the patient's medical chart.

All patients who are excluded due to one or more criteria listed above will be treated for their headache symptoms according to standard clinical practices, which may include EBP, SPGB or other block, or medical management as the clinical situation dictates. An anesthesiologist or a physician in another department may perform these procedures according to institutional practices. Exclusion from this study will not in any way prevent a patient with PDPH from receiving the treatment he or she would have otherwise received.

